##### Evaluable Non-Target Disease Response

Patients who have lesions present at baseline that are evaluable but do not meet the definitions of measurable disease, have received at least one cycle of therapy, and have had their disease re-evaluated will be considered evaluable for non-target lesion assessment. The response assessment is based on the presence, absence, or unequivocal progression of the lesions.

---

6.1.2 Disease Parameters

Measurable Disease

Measurable lesions are defined as those that can be accurately measured in at least one dimension (longest diameter to be recorded) as  $\geq 20$  mm by chest x-ray, as  $\geq 10$  mm with CT scan, or  $\geq 10$  mm with calipers by clinical exam. All tumor measurements must be recorded in millimeters.

**NOTE:** Tumor lesions that are situated in a previously irradiated area may only be considered measurable if there is evidence of post-radiation progression.

Malignant Lymph Nodes

To be considered pathologically enlarged and measurable, a lymph node must be  $\geq 15$  mm in short axis when assessed by CT scan (CT scan slice thickness recommended to be no greater than 5 mm). At baseline and in follow-up, only the short axis will be measured and followed.

Non-measurable Disease

All other lesions (or sites of disease), including small lesions (longest diameter  $< 10$  mm or pathological lymph nodes with  $\geq 10$  to  $< 15$  mm short axis), are considered non-measurable disease. Bone lesions, leptomeningeal disease, ascites, pleural/pericardial effusions, lymphangitis cutis/pulmonitis, inflammatory breast disease, and abdominal masses (not followed by CT or MRI), are considered as non-measurable. Non-measurable also includes lesions that are  $< 20$  mm by chest x-ray.

**NOTE:** Cystic lesions that meet the criteria for radiographically defined simple cysts should not be considered as malignant lesions (neither measurable nor non-measurable) since they are, by definition, simple cysts.

'Cystic lesions' thought to represent cystic metastases can be considered as measurable lesions, if they meet the definition of measurability described above. However, if non-cystic lesions are present in the same patient, these are preferred for selection as target lesions.

Target Lesions

All measurable lesions up to a maximum of 2 lesions per organ and 5 lesions in total, representative of all involved organs, should be identified as **target lesions** and recorded and measured at baseline. Target lesions should be selected on the basis of their size (lesions with the longest diameter), be representative of all involved organs, but in addition should be those that lend themselves to reproducible repeated measurements. It may be the case that, on occasion, the largest lesion does not lend itself to reproducible measurement in which circumstance the next largest lesion which can be measured reproducibly should be selected.

A sum of the diameters (longest for non-nodal lesions, short axis for nodal lesions) for all target lesions will be calculated and reported as the baseline sum diameters. If lymph nodes are to be included in the sum, then only the short axis is added into the sum. The baseline sum of the diameters will be used as reference to further characterize any objective tumor regression in the measurable dimension of the disease.

#### Non-target Lesions

All other lesions (or sites of disease) including any measurable lesions over and above the 5 target lesions should be identified as non-target lesions and should also be recorded at baseline. Measurements of these lesions are not required, but the presence or absence of unequivocal progression of each should be noted throughout follow-up.

#### 6.1.3 Methods for Evaluation of Disease

All measurements should be taken and recorded in metric notation using a ruler or calipers. All baseline evaluations should be performed as closely as possible to the beginning of treatment and never more than 4 weeks before randomization.

The same method of assessment and the same technique must be used to characterize each identified and reported lesion at baseline and during follow-up. Imaging-based evaluation is preferred to evaluation by clinical examination unless the lesion(s) being followed cannot be imaged but are assessable by clinical exam.

#### Clinical Lesions

Clinical lesions will only be considered measurable when they are superficial (e.g., skin nodules and palpable lymph nodes) and  $\geq 10$  mm in diameter as assessed using calipers (e.g., skin nodules). In the case of skin lesions, documentation by color photography, including a ruler to estimate the size of the lesion, is recommended.

#### Chest X-ray

Lesions on chest x-ray are acceptable as measurable lesions when they are clearly defined and surrounded by aerated lung. However, CT is preferable.

#### Conventional CT and MRI

This RECIST 1.1 guideline has defined measurability of lesions on CT scan based on the assumption that CT slice thickness is 5 mm or less. If CT scans have slice thickness greater than 5 mm, the minimum size for a measurable lesion should be twice the slice thickness. MRI is also acceptable in certain situations (e.g. for body scans).

Diagnostic quality CT is preferred (with oral and IV contrast); any deviations from this must be approved by the Study Chair in advance. See note below regarding contrast allergy.

---

Use of MRI remains a complex issue. MRI has excellent contrast, spatial, and temporal resolution; however, there are many image acquisition variables involved in MRI which greatly impact image quality, lesion conspicuity, and measurement. Furthermore, the availability of MRI is variable globally. As with CT, if an MRI is performed, the technical specifications of the scanning sequences used should be optimized for the evaluation of the type and site of disease. Furthermore, as with CT, the modality used at follow-up must be the same as was used at baseline and the lesions should be measured/assessed on the same pulse sequence. It is beyond the scope of the RECIST guidelines to prescribe specific MRI pulse sequence parameters for all scanners, body parts, and diseases. Ideally, the same type of scanner should be used and the image acquisition protocol should be followed as closely as possible to prior scans. Body scans should be performed with breath-hold scanning techniques, if possible.

**NOTE:** If prior to enrollment it is known a patient is not able to undergo CT scans with IV contrast due to allergy or renal insufficiency, the decision as to whether a non-contrast CT or MRI (with or without IV contrast) should be used to evaluate the subject at baseline and follow-up should be guided by the anatomic location(s) of the disease. For patients who develop contraindications to contrast after baseline contrast CT is done, the decision as to whether non-contrast CT or MRI (enhanced or non-enhanced) should be performed should also be based on the anatomic location of the disease and should be optimized to allow for comparison to the prior studies if possible. Each case should be discussed with the radiologist and Protocol Chair/designee to determine if substitution of these other approaches is possible and, if not, the patient may be considered not evaluable from that point forward.

#### PET-CT

At present, the low dose or attenuation correction CT portion of a combined PET-CT is not always of optimal diagnostic CT quality for use with RECIST measurements. However, if the site can document that the CT performed as part of a PET-CT is of identical diagnostic quality to a diagnostic CT (with IV and oral contrast), then the CT portion of the PET-CT can be used for RECIST measurements and can be used interchangeably with conventional CT in accurately measuring cancer lesions over time.

#### Ultrasound

Ultrasound is not useful in assessment of lesion size and should not be used as a method of measurement. Ultrasound examinations cannot be reproduced in their entirety for independent review at a later date and, because they are operator dependent, it cannot be guaranteed that the same technique and measurements will be taken from one assessment to the next. If new lesions are identified by

ultrasound in the course of the study, confirmation by CT or MRI is advised. If there is concern about radiation exposure at CT, MRI may be used instead of CT in selected instances.

#### Endoscopy, Laparoscopy

The utilization of these techniques for objective tumor evaluation is not advised. However, such techniques may be useful to confirm complete pathological response when biopsies are obtained or to determine relapse in trials where recurrence following complete response (CR) or surgical resection is an endpoint.

#### Tumor Markers

Tumor markers alone cannot be used to assess response. If markers are initially above the upper normal limit, they must normalize for a patient to be considered in complete clinical response.

#### Cytology, Histology

These techniques can be used to differentiate between partial responses (PR) and complete responses (CR) in rare cases (e.g., residual lesions in tumor types, such as germ cell tumors, where known residual benign tumors can remain).

### 6.1.4 Response Criteria

#### 6.1.4.1 Evaluation of Target Lesions

##### Complete Response (CR)

Disappearance of all target lesions. Any pathological lymph nodes (whether target or non-target) must have reduction in short axis to < 10 mm.

##### Partial Response (PR)

At least a 30% decrease in the sum of the diameters of target lesions, taking as reference the baseline sum diameters

##### Progressive Disease (PD)

At least a 20% increase in the sum of the diameters of target lesions, taking as reference the smallest sum on study (this includes the baseline sum if that is the smallest on study). In addition to the relative increase of 20%, the sum must also demonstrate an absolute increase of at least 5 mm.

**NOTE:** The appearance of one or more new lesions is also considered progression. See Section [6.1.4.3](#).

##### Stable Disease (SD)

Neither sufficient shrinkage to qualify for PR nor sufficient increase to qualify for PD, taking as reference the smallest sum diameters while on study. (Note: a change of 20% or

more that does not increase the sum of the diameters by 5 mm or more is coded as stable disease)

To be assigned a status of stable disease, measurements must have met the stable disease criteria at least once after study entry at a minimum interval of 12 weeks.

#### 6.1.4.2 Evaluation of Non-Target Lesions

##### Complete Response (CR)

Disappearance of all non-target lesions. All lymph nodes must be non-pathological in size (< 10 mm short axis)

##### Non-CR/Non-PD

Persistence of one or more non-target lesions.

##### Progressive Disease (PD)

Appearance of one or more new lesions and/or unequivocal progression of existing non-target lesions (see Section [6.1.4.3](#)). Unequivocal progression should not normally trump target lesion status. It must be representative of overall disease status change, not a single lesion increase.

When the patient also has measurable disease, there must be an overall level of substantial worsening in non-target disease such that, even in the presence of SD or PR in target disease, the overall tumor burden has increased sufficiently to merit discontinuation of therapy. A modest “increase” in the size of one or more non-target lesions is usually not sufficient to qualify for unequivocal progression status. The designation of overall progression solely on the basis of change in non-target disease in the face of SD or PR of target disease will therefore be extremely rare.

When the patient only has non-measurable disease, the increase in overall disease burden should be comparable in magnitude to the increase that would be required to declare PD for measurable disease: i.e., an increase in tumor burden from “trace” to “large”, an increase in nodal disease from “localized” to “widespread”, or an increase sufficient to require a change in therapy.

Although a clear progression of “non-target” lesions only is exceptional, the opinion of the treating physician should prevail in such circumstances, and the progression status should be confirmed at a later time by the review panel.

#### 6.1.4.3 Evaluation of New Lesions

The appearance of new lesions constitutes Progressive Disease (PD).

A growing lymph node that did not meet the criteria for reporting as a measurable or non-measurable lymph node

at baseline should only be reported as a new lesion (and therefore progressive disease) if it: a) increases in size to  $\geq 15$  mm in the short axis, or b) there is new pathological confirmation that it is disease (regardless of size).

#### 6.1.4.4 Evaluation of Best Overall Response

The best overall response is the best response recorded from the start of the treatment until disease progression/recurrence (taking as reference for progressive disease the smallest measurements recorded since the treatment started). The patient's best response assignment will depend on the achievement of both measurement and confirmation criteria.

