### 2.2 Secondary Objectives

- 2.2.1 To evaluate the safety and tolerability of entinostat in combination with exemestane, and to compare the safety profile to that of endocrine therapy with placebo.
- 2.2.2 To evaluate the objective response rate of exemestane in combination with entinostat or placebo.
- 2.2.3 To evaluate whether the efficacy of exemestane with entinostat varies with changes in acetylation status in peripheral blood mononuclear cells (PBMCs).
- 2.2.4 To evaluate the time to treatment deterioration (as defined by decrease in HRQL, progression, death) of exemestane + entinostat versus exemestane + placebo arms.
- 2.2.5 To evaluate the differences in overall health-related quality of life (HRQL) between the exemestane + entinostat versus exemestane + placebo arms.
- 2.2.6 To evaluate the difference with respect to specific symptoms that are associated with entinostat, i.e., fatigue, nausea, anorexia and diarrhea, between the exemestane + entinostat versus exemestane + placebo arms.
- 2.2.7 To measure adherence to protocol therapy.
- 2.2.8 To evaluate the pharmacokinetics of entinostat in patients with advanced breast cancer.
- 2.2.9 To evaluate what, if any, patient variables alter the pharmacokinetic profile of entinostat in patients with advanced breast cancer.

Rev.10/16

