#### 5.8 Duration of Follow-up

For this protocol, all patients, including those who discontinue protocol therapy early, will be followed for response until progression even if non-protocol therapy is initiated. Upon discontinuation of treatment, patients will be followed for survival per the standard ECOG-ACRIN follow-up schedule: Every 3 months if patient is < 2 years from study entry, every 6 months if patient is 2-5 years from study entry, and every 12 months if patient is > 5 years from study entry for up to 10 years, including patients removed from study for unacceptable adverse events.

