### 9.3 Statistical Consideration for Objective Response, Toxicity and Time to Treatment Deterioration

#### 9.3.1 Objective response

Objective response in the two arms will be evaluated by comparing objective response rate (ORR, PR+CR) using a Fisher's exact test on the intention-to-treat patients with one-sided type I error of 2.5%. The primary analysis of ORR will be evaluated on the first 360 patients enrolled for the PFS analysis, a secondary analysis of ORR will be conducted on all patients. Patients who are unevaluable for response and patients never starting protocol therapy will be included as non-responders in this analysis. Based on the BOLERO-2 results, the ORR will be about 0.4% on arm B. For the primary analysis of objective response, with 180 refractory patients on each arm, the study will have 86% power to detect an increase to a 6% objective response rate on arm A.

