Tumor response will be assessed per Response Evaluation Criteria In Solid Tumors (RECIST) version 1.1 following the standard ECOG-ACRIN review procedures. PFS is defined to be time from randomization to the earliest documented disease progression as defined by the RECIST criteria, new primary breast cancer, or death without progression. Disease assessment will continue until disease progression, even after non-protocol anti-cancer therapy is started. Cases with incomplete follow up or without adequate disease evaluations will be censored at the date last documented to be free of progression, regardless of whether non-protocol anti-cancer therapy is started or not. As a sensitivity analysis, PFS will also be defined in the following ways: 1) Considering the start of a new non-protocol anti-cancer therapy as a PFS event, in addition to disease progression, new primary breast cancer and death without progression. 2) Censoring PFS observation at the last assessment before a new non-protocol anti-cancer therapy is started for the patients who start new anti-cancer therapy without a documented PFS event. OS is defined to be time from randomization to death from any cause. Cases who are still alive will be censored at the date last known alive. ORR is defined as the proportion of patients with complete response (CR) or partial response (PR) among all patients (including patients with unevaluable tumor response).

All primary analyses regarding PFS, OS and ORR will be based on intention-to-treat population regardless of eligibility status. A secondary analysis for PFS, OS and ORR will be conducted in eligible patients. The distributions of PFS and OS will be estimated using the Kaplan- Meier method (1958), with 95% confidence intervals calculated using Greenwood's formula. In the primary analyses of PFS and OS, differences in treatment effect will be tested using stratified log rank tests, stratifying on the randomization stratification factors. Stratified univariate and multivariable Cox proportional-hazard models (1972) will be built to estimate the hazard ratios (HRs) for treatment effect for PFS and OS as a supportive analysis. In the multivariable Cox models, known prognostic factors will be included as covariates when appropriate, such as age at diagnosis, race/ethnicity, body mass index (BMI), ECOG performance status, disease stage

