10.2 Independent Imaging Review

The independent imaging review will be conducted only on the first 360-participants-enrolled cohort identified for the primary endpoint analysis. Radiologist readers will review each case's series of imaging studies to identify progression using RECIST 1.1 criteria. Independent readers will be blinded to

local radiologist findings. Local reads will be used to define progression for study-related treatment decisions.

Subject scans will be considered ready for independent image review once the following occurs:

- Applicable Baseline clinical data available; and
- Baseline and one on-study time point available and acceptable; and
- Subject has completed all imaging visits; or
- Subject is off-treatment; or
- Sponsor (or designee)-defined cutoff, if applicable.

For each subject, the time point-by-time point imaging response evaluation will be performed by two (2) independent, qualified, and approved radiologist reviewers in a sequential locked-read paradigm. Neither primary reviewer will have access to the other reviewer's annotations or tumor response data. Baseline clinical data, if applicable, will be provided.

Rev.10/15

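### A tumor response first seen on non-protocol anticancer therapy, before progression, counts toward the randomized arm's ORR; the plan handles new therapy for PFS only

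*Combined protocol and SAP*

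**What the plan says.** - **Follow-up (Section 5.8).** All patients, including those who stop protocol therapy early, "will be followed for response until progression even if non-protocol therapy is initiated". Section 9.4 repeats the point: "Disease assessment will continue until disease progression, even after non-protocol anti-cancer therapy is started".
- **Response window (Section 6.1.4.4).** "The best overall response is the best response recorded from the start of the treatment until disease progression/recurrence". Starting another drug does not close it.
- **Endpoint (Section 9.4).** "ORR is defined as the proportion of patients with complete response (CR) or partial response (PR) among all patients".
- **Non-responder rule (Section 9.3.1).** "Patients who are unevaluable for response and patients never starting protocol therapy will be included as non-responders in this analysis". No other non-responder rule is given.
- **New therapy (Section 9.4).** Two sensitivity analyses deal with it. One counts it as an event; the other is described as "Censoring PFS observation at the last assessment before a new non-protocol anti-cancer therapy is started". Both concern PFS. There is no counterpart for ORR.
- **Objective 2.2.2.** "To evaluate the objective response rate of exemestane in combination with entinostat or placebo".
- **Central readers (Section 10.2).** "Baseline clinical data, if applicable, will be provided". No later clinical information, such as a change of therapy, is mentioned.

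**The concern.** Patients can leave protocol treatment without RECIST progression in several ways that the protocol itself lists: toxicity, omitted doses or a long exemestane hold (Sections 5.4 and 5.7), unblinding (Section 4.7) or symptomatic deterioration (Section 6.1.4.4). Off-treatment imaging then continues until progression (Section 10.1.12). If such a patient starts another anticancer drug and reaches a PR on it, the plan scores a response for the randomized arm.

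That response does not measure the regimen named in objective 2.2.2. Section 5.7 itself treats receipt of non-protocol therapy as the end of protocol treatment. Because almost no control responses are expected, even a small number of borrowed ones can change the comparison. Spread equally over both arms, they dilute a real difference. Concentrated in one arm, they can add to or hide one.

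**Working it through.** **Inputs from Section 9.3.1.** 180 patients per arm; ORR 0.4% on arm B and 6% on arm A; Fisher's exact test, one-sided 2.5%; stated power 86%. Expected responders: 180 × 0.004 = 0.72 on arm B and 180 × 0.06 = 10.8 on arm A.

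**Reproducing the plan's figure.** Enumerating all binomial outcomes and rejecting when the hypergeometric tail is at most 0.025 gives power 86.2%. The stated 86% is correct on its own inputs. The test rejects with 6 responders on arm A against 0 on arm B, 8 against 1, or 10 against 2. Each of the first two control responses therefore raises the bar by two.

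**Adding later-therapy responses.** Let f be the share of an arm that starts non-protocol therapy before progression, r the response rate to it, and p the ORR on protocol therapy. The counted ORR is

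p + (1 − p) × f × r.

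The documents give neither f nor r for this situation; both are assumptions. The lower r of 7% is the figure that Section 1.2 quotes for second-line hormonal therapy. The upper 20% is close to the 19% that Section 1.3.4 quotes for vorinostat plus tamoxifen.

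*Example, f = 5% and r = 7% in both arms:* arm B 0.004 + 0.996 × 0.0035 = 0.75%; arm A 0.06 + 0.94 × 0.0035 = 6.33%.

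*Equal f in both arms, true rates 0.4% and 6%:*

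| f | r | Counted ORR, B vs A | Power |
|---|---|---|---|
| none | – | 0.4% vs 6.0% | 86.2% |
| 5% | 7% | 0.75% vs 6.3% | 79.6% |
| 5% | 10% | 0.9% vs 6.5% | 77.0% |
| 5% | 20% | 1.4% vs 6.9% | 69.5% |
| 10% | 10% | 1.4% vs 6.9% | 69.5% |
| 10% | 20% | 2.4% vs 7.9% | 58.5% |

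*No entinostat effect (true ORR 0.4% in both arms), unequal f.* The last column multiplies f × r by 0.8, because Sections 6.1 and 9.2 plan for about 20% of patients with non-measurable disease only, and Section 6.1.1 limits evaluability for objective response to measurable disease.

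| f, A vs B | r | Rejection rate, all 180 can contribute | Rejection rate, 80% can contribute |
|---|---|---|---|
| 10% vs 5% | 7% | 0.4% | 0.3% |
| 10% vs 5% | 10% | 1.0% | 0.6% |
| 10% vs 5% | 20% | 3.8% | 2.6% |
| 15% vs 5% | 7% | 1.4% | 0.8% |
| 15% vs 5% | 10% | 3.3% | 2.0% |
| 15% vs 5% | 20% | 12.8% | 8.7% |

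With no added responses the rejection rate is below 0.1%, because Fisher's test is very conservative at these rates. That leaves room for some contamination before the nominal 2.5% is exceeded.

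**If the window closes at new therapy,** the planning rates apply again and power returns to 86.2%. No stated figure needs to change.

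**The case against.** **It is a choice of estimand.** ORR is analyzed by intention to treat, and counting outcomes whatever is given later is a coherent policy that matches PFS. This stands for PFS. For ORR the plan does not follow it consistently: a patient who never starts protocol therapy and responds to chemotherapy is a non-responder, while one who stops after a cycle and responds to the same chemotherapy is a responder. The ORR text does not present this as deliberate.

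**The size may be small.** Much of this stands. Control PFS is expected to be 4.1 months (Section 9.2.1), so many patients progress, which closes the window, before any switch. A PR needs a 30% fall from the protocol baseline (Section 6.1.4.1), not from the start of the new drug. Section 5.4 lets exemestane continue for some patients stopped for entinostat/placebo toxicity. With f = 15% vs 5%, r = 7% and the planned 6% effect, power is 86.3%, essentially unchanged.

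**A rule may exist elsewhere.** Section 9.4 refers to the group's own review procedures for response. They are not in the documents and could contain a cut-off. This limits confidence.

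**Stronger readings to avoid.** A reader might infer that a false-positive ORR result is likely. The documents supply neither f nor r, and the modest cases stay below 2.5%. A reader might also take as f the 24% vs 5% permanent discontinuation rates that Section 1.3 gives for everolimus and its placebo. Those are stops for adverse reactions to a different drug, not starts of new anticancer therapy before progression, and Section 1.5 describes entinostat as generally well tolerated.

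**Conclusion.** The gap is real on the text: as written, a CR or PR first recorded after non-protocol therapy starts but before progression counts for the randomized arm, and this does not match objective 2.2.2. Under the assumed equal f of 5-10% and r of 7-20%, power drops from 86% to about 58-80%. Inflation of the false-positive rate is conditional. It is absent in the modest cases and appears with a large arm imbalance, a high r, or both. At f = 15% vs 5% and r = 20% it reaches 12.8%, or about 9% if only patients with measurable disease can contribute. All of these sizes rest on assumed f and r.

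The plan should be changed, but the consequence is bounded. ORR is a secondary endpoint, and the primary PFS and OS analyses are not affected. Confidence is moderate, given the review procedures that cannot be seen.

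**What to change.** In Sections 6.1.4.4, 9.3.1 and 9.4, define best overall response for ORR as the best response recorded from randomization until the earlier of progression or the start of non-protocol anticancer therapy. Patients without a CR or PR by then are non-responders, alongside the never-starters and unevaluable patients already covered. Use the same definition of non-protocol therapy as in the PFS sensitivity analyses, and the same cut-off for the response comparison in Section 9.5.2. Leave PFS follow-up as it is. Counting every response to progression can be reported as a sensitivity analysis. If the group's review procedures already set such a cut-off, stating it here is enough.

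**Cost.** Wording only. The start date of non-protocol therapy is already needed for the PFS sensitivity analyses, so no new data are required. The observed ORR may be slightly lower. Section 9 plans no duration-of-response analysis, so no planned result there is affected.
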